8.2 Data processing

To ensure the consistency of data collection across clinics, relevant definitions, terminology used and descriptions of procedures will be described in a data manual (RESCOM Dataset Handbook) available to all local study coordinators (LSC). The LSC will be supervised by the Central Study Coordination (CSC) to guarantee adherence to standard operation procedures. The LSC will enable real time monitoring of enrolment of participants to CSC to early identify difficulties. Data storage, validation, monitoring, update, backup and analysis will be performed centrally at the CSC following established procedures. The CSC is hosted by Clinical Trial Unit of the Swiss Paraplegic Centre in Nottwil.

All study data from RESCOM are encrypted. Personal data of participants will be stored in the local clinic database. Both study data and personal data will contain a unique identifier (RESCOM ID number) allowing to link the datasets when needed. For all data analyses, only the encrypted research data set (study data) will be used. Personal data will only be used for local administration and follow-up of participants.

Statistical procedures in data processing will be to derive descriptive statistics for the distributions of each of the variables of interest, which will also be used to check for outlying observations and data errors. In addition, pairwise associations between variables of interest will be evaluated and possible errors will be checked with the local center and data values will be corrected where possible, or else coded as missing. Outlying observations that cannot be confirmed to be errors will be left as originally coded. Descriptive graphical and statistical methods at these early stages of analyses will include histograms, scatter plots and cumulative frequency distributions, one-way and two-way tables with appropriate percentages, Pearson's $\chi 2$ and/or Fisher's exact test for association in contingency tables, t-tests and/or Wilcoxon Rank Sum test for comparison of numerical variables between two groups, and Pearson correlations and simple linear regression models. For continuous secondary outcomes (e.g., several parameters of respiratory function) the distribution of residuals of linear regression analyses will be evaluated for overall skew and systematic spread with the values of dependent variables of interest ("heteroscedasticity") as to derive appropriate transformations that remove skew and achieve approximate "homoscedasticity."

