To evaluate the diagnostic accuracy of markers of lung function (particularly MIP) for predicting or excluding clinical pneumonia we will use contemporary receiver operating characteristic (ROC) analyses techniques that allow for adjusting of covariate effects (21). Such adjustments principally facilitate an unbiased estimate of pneumonia classification accuracy of potential marker(s) by controlling for the effects of other factors, such as for instance individual patient characteristics, disease traits, or site-specific features of measurement or diagnostic procedures. In case covariates affect discrimination (i.e., the ROC curve), nonparametric and parametric estimators have been proposed and implemented as to combine marker and covariate information in describing the improvement in discriminatory accuracy (21-23). Importantly, these methodologies thus also support the evaluation of adjusted ROC curves by individual patient characteristics (e.g., gender, age) or SCI characteristics (e.g., lesion level, lesion completeness, temporary or permanent artificial ventilation).

Regression modelling of secondary outcomes

Analyses of secondary outcomes will make use of common regression models, or extensions of these models. The choice of regression model will be determined by the statistical nature of the secondary outcome variable, in particular its error distribution (19). We thus anticipate using multiple regression for the modelling of the lung parameters MIP, MEP, FVC, FEV₁ and PEF, if needed using appropriate transformations as to meet normality assumptions. In case a normal error distribution is not achieved,

the outcome variable will be converted into a ordinal variable with multinomial categorical outcomes using clinically-relevant cut-offs and analysed using ordinal regression or stereotype regression, the latter in case of failure to meet proportional odds assumptions (24-26). Alternatively, a binary cut-off combined with logistic regression analysis may be used.

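### Section 8.2 judges unequal variance by residual spread against the dependent variable, a check that can give false signals in clean data and prompt needless transformation of the lung-function outcomes

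*Combined protocol and SAP*

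**What the plan says.** Section 8.2 (Data processing) covers the continuous secondary outcomes, with respiratory function parameters as its example. It has the residuals of the linear regressions checked for skew and for "systematic spread with the values of dependent variables of interest", and labels such spread heteroscedasticity. The purpose is stated: "as to derive appropriate transformations that remove skew and achieve approximate" homoscedasticity. The section names no test, threshold or particular graph for this check, and mentions neither fitted values nor predictors in connection with it.

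Section 8.3.2 (Regression modelling of secondary outcomes) foresees "multiple regression for the modelling of the lung parameters MIP, MEP, FVC", FEV1 and PEF, "if needed using appropriate transformations as to meet normality assumptions". A later step has its own condition: "In case a normal error distribution is not achieved", then "the outcome variable will be converted into a ordinal variable with multinomial categorical outcomes using clinically-relevant cut-offs", with a binary cut-off as an alternative.

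Under the heading on predictors, section 8.3.2 lists the main predictors as AIS grade, paraplegia or tetraplegia, PCF and partial ventilator dependency. Three of these four are categorical.

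**The concern.** Equal error variance is a statement about the errors given the predictors. It is checked by seeing whether residual spread changes with the fitted values or with a predictor. The observed outcome contains the residual, so residuals set against it show a pattern whether or not the variance is equal. An analyst who follows section 8.2 literally may take that pattern for heteroscedasticity and transform an outcome that needed no transformation.

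What is at stake is the scale of the secondary results. The lung-function outcomes are read clinically in their own units, and a needless transformation moves the estimated effects off those units. Because section 8.2 ties transformation to this check, a false signal has a stated consequence.

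**Working it through.** The plan gives no figure for this check, so there is none to reproduce.

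**Inputs.** From the plan: 625 patients (section 8.1) and significance level 0.05 (section 8.3). Assumed, because the plan does not give them: R2 of 0.1, 0.3, 0.5 and 0.7, and the predictor distributions.

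**Step 1: the built-in correlation.** Write e = Y - F, with F the fitted value. Least squares with an intercept makes e uncorrelated with F. Hence Cov(e, Y) = Var(e) = (1 - R2) Var(Y), and

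corr(e, Y) = Var(e) / [SD(e) SD(Y)] = sqrt(1 - R2).

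For R2 = 0.1, 0.3, 0.5 and 0.7 this is 0.95, 0.84, 0.71 and 0.55. The correlation of e with F is 0.

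**Step 2: the spread at a given outcome value.** At a fixed Y = y, e = y - F, so Var(e | y) = Var(F | y). Residual spread across the outcome is thus the spread of the fitted values among patients who share that outcome.
- Normal predictor, Var(Y) = 1: Var(e | y) = R2(1 - R2), the same at every y. The residual mean shifts with y; the spread around it does not.
- One binary predictor, split 50:50, R2 = 0.7: the group means differ by sqrt(0.7/0.25) = 1.67. Where the groups overlap equally, the SD of e is 1.67/2 = 0.84; far out, where only one group is left, it falls towards 0. The true error SD is sqrt(0.3) = 0.55 throughout.

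**Step 3: simulation.** Correctly specified linear model, normal errors of equal variance, 625 patients, 500 runs per setting. Squared residuals were regressed on the stated variable (Koenker/Breusch-Pagan test, 0.05 level). Ranges run over the four R2 values.

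| Share of runs rejecting | Normal predictor | One binary | Three binary |
|---|---|---|---|
| Against observed Y, linear term | 14-27% | 9-28% | 14-20% |
| Against observed Y, linear + quadratic | 100% | 100% | 100% |
| Same, built-in trend removed first | 4.2-5.8% | 98-100% | 29-66% |
| Against fitted values, linear term | 4.0-6.4% | 3.8-5.4% | 4.0-5.4% |
| Against fitted values, linear + quadratic | 4.4-5.8% | cannot be fitted | 4.4-5.6% |
| Shapiro-Wilk test of residual normality | 4.4-6.4% | 5.0-6.4% | 4.4-6.6% |

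Mean residual SD by fifth of the outcome, one binary predictor, R2 = 0.7: 0.31, 0.31, 0.73, 0.30, 0.31. This unevenness arises with equal error variance, as step 2 predicts.

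A second simulation used predictors modelled on those in section 8.3.2, again with assumed distributions, 625 patients and R2 of 0.1 to 0.7. Residual-outcome correlation ran from 0.94 down to 0.54. Tests against the observed outcome rejected in 11-24% of runs (linear) and 100% (quadratic), against 4-6% for fitted values. Shapiro-Wilk again rejected in 4-6%.

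**The case against.** **Much of the pattern is a trend, not spread.** This stands for a normal predictor. At R2 = 0.3 the root-mean-square residual is sqrt(0.21) = 0.46 at the outcome mean and sqrt(0.21 + 1.40²) = 1.47 at 2 SD from it. A reader might infer a 3.2-fold change in spread. It is not one: the residual SD is 0.46 at both places, and only the residual mean moves, from 0 to 1.40. The 100% for the quadratic test with a normal predictor reflects that shift, and rejection returns to 4.2-5.8% once the trend is removed. The defence does not carry over to categorical predictors, where the spread itself is uneven, and most of the plan's main predictors are categorical.

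**No test or threshold is set.** This also stands. A reader might infer that the check *would* force transformation in essentially every model. The documents do not support that: how often an analyst would act depends on how the spread is judged, and a linear test gives far fewer false signals than a quadratic one. No transformation decision was simulated. The check *can* mislead; how often it will is unknown.

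**Grouping has a different trigger.** A reader might infer that the check also pushes lung-function outcomes into categories, with loss of information. Section 8.3.2 makes that step depend on non-normal errors, and the normality test kept about its nominal error rate in the same data. A badly chosen transformation could itself produce non-normal residuals, but nothing in the plan obliges the analyst to keep it, so the plan does not make grouping a consequence of this check.

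**It may be a slip.** The phrase may have been meant as independent variables or predicted values. The documents cannot settle this. Either way it is the only instruction given for this check, and no other section corrects it.

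**Conclusion.** The point holds as an error in a stated diagnostic rule, minor in reach. Read literally, section 8.2 judges residual spread against a variable that contains the residual, and links the result to transformation. In data with nothing wrong, variance tests on that basis rejected in about 11-24% (linear) to 100% (quadratic) of runs with predictors like the plan's, against about 4-6% for fitted values. The correlation sqrt(1 - R2) is algebra and needs no distributional assumption. The rejection rates rest on assumed R2 values and predictor distributions, on tests the plan does not name, and on one independent record per patient; clustering and repeated visits were not simulated.

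Only the secondary lung-function regressions are touched. The primary ROC analysis does not use this check, and neither certain transformation nor automatic grouping follows from the text.

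**What to change.** In section 8.2, where the text reads "systematic spread with the values of dependent variables of interest", replace what follows the word *with* by *fitted values and each predictor*. Add that the residuals are those of the model actually fitted, since section 8.3.2 expects mainly random-effects models for the hierarchical data.

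The cost is one phrase in the analysis text. No data collection, sample size or primary analysis changes. If the present wording is a slip, the edit only records what was meant.

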8.3 Planned analysis (STROBE 12a-d)

Statistical significance will be set at alpha ≤ 0.050. All statistical analyses will be performed using STATA (Version 14.1, StataCorp, Texas, USA), R (Version 3.2.1, The R Foundation for Statistical Computing) or SPSS (Version 18.0.3, IBM, Somers, NY, USA).

8.3.1 Descriptive analysis

Descriptive statistics involving demographic data, lesion characteristics, life style characteristics, medication and vaccination, partly mechanical ventilation dependency, smoking, respiratory muscle

training and physical exercise as well as primary and secondary outcome parameters will be presented as mean (standard deviation) and median (25% and 75% quartile) or frequency (binomial 95% confidence interval), where appropriate. Descriptive statistics will be provided for the overall sample as well as stratified for the two groups that are discriminated by the event of at least one event of pneumonia during the study period.

8.3.2 Advanced regression modelling of primary and secondary outcomes

General principles

Univariable and multivariable regression modelling will be used to evaluate the primary outcome and secondary outcomes. Multivariable modelling as compared univariable modelling will principally allow us to investigate relative contribution of different predictors (or risk factors) to the outcome of interest, while controlling for potential confounding by other factors. To evaluate and eliminate confounding stratified models may also be used. Multivariable models may further be used to examine effect modification (interaction) as well as mediation (intervening variables that are on the causal pathway between a predictor and the outcome of interest) (19). The choice of regression model will be determined by the nature of the primary outcome and secondary outcomes (e.g., multivariable ROC analysis for diagnostic accuracy; multiple regression models for continuous variables, logistic regression models for dichotomous variables, and flexible parametric survival models for mortality data) as described in detail below.

Dealing with the hierarchical data structure (i.e., repeated measures for participants nested within clinics or countries) will be a fundamental issue in RESCOM analyses. The most basic means of dealing with such structure is to use extensions of the regression models listed above that allow for clustering of outcomes between individuals in the same cohort. The most important aim of analyses that allow for hierarchical data structures is to ensure that standard errors of regression coefficients are valid (since these will be too small if hierarchical data structures are ignored). Hierarchical analyses of RESCOM data will mainly use random-effects regression models allowing for sources of heterogeneity that may arise at the group (and/or individual) level (19, 20).

Regression modelling of primary outcome

To evaluate the diagnostic accuracy of markers of lung function (particularly MIP) for predicting or excluding clinical pneumonia we will use contemporary receiver operating characteristic (ROC) analyses techniques that allow for adjusting of covariate effects (21). Such adjustments principally facilitate an unbiased estimate of pneumonia classification accuracy of potential marker(s) by controlling for the effects of other factors, such as for instance individual patient characteristics, disease traits, or site-specific features of measurement or diagnostic procedures. In case covariates affect discrimination (i.e., the ROC curve), nonparametric and parametric estimators have been proposed and implemented as to combine marker and covariate information in describing the improvement in discriminatory accuracy (21-23). Importantly, these methodologies thus also support the evaluation of adjusted ROC curves by individual patient characteristics (e.g., gender, age) or SCI characteristics (e.g., lesion level, lesion completeness, temporary or permanent artificial ventilation).

Regression modelling of secondary outcomes

Analyses of secondary outcomes will make use of common regression models, or extensions of these models. The choice of regression model will be determined by the statistical nature of the secondary outcome variable, in particular its error distribution (19). We thus anticipate using multiple regression for the modelling of the lung parameters MIP, MEP, FVC, FEV₁ and PEF, if needed using appropriate transformations as to meet normality assumptions. In case a normal error distribution is not achieved,

the outcome variable will be converted into a ordinal variable with multinomial categorical outcomes using clinically-relevant cut-offs and analysed using ordinal regression or stereotype regression, the latter in case of failure to meet proportional odds assumptions (24-26). Alternatively, a binary cut-off combined with logistic regression analysis may be used.

For the analysis of all-cause and pneumonia-related mortality flexible parametric survival models will be applied that allow for a flexible approach in modelling and estimation of the baseline hazard of death (27, 28). Survival time will start at the date of initiation of first rehabilitation and censoring is at date of discharge from local first rehabilitation or at date of death. The analysis of pneumonia-related mortality will be adjusted for competing risks, i.e., events that either hinder the observation of the event of interest or modifies the chance that this event occurs. Potential competing risks for the event of pneumonia-related mortality during first SCI rehabilitation for instance include other causes of mortality (e.g., septicaemia, neoplasm) or transfer to another rehabilitation clinic or another facility to receive specialized treatment. In such cases the censored time-to-events reflect a form of incomplete data that may induce bias in estimates of pneumonia risk from unadjusted analyses. Competing risk analysis accounts for competing events as to provide an unbiased estimate of the pneumonia-related hazard of death during first rehabilitation (29, 30).

Predictors; extraneous, mediating, moderating and confounding variables

The main predictors (exposures of interest) in the modelling of the primary outcome and secondary outcomes include the degree of motor and sensory neurological impairment as captured by the ASIA Impairment Scale (35); lesion level classified as paraplegia or tetraplegia; PCF and partial dependency on mechanical ventilation (a minimum of 1hour free of ventilator dependency during the day). Further predictors for secondary outcomes include an index of physical activity as well as an indicator for respiratory training, assessed using a questionnaire.

Likely extraneous variables (affecting either the exposure or the outcome) or confounding variables (affecting both the exposure and the outcome) comprise gender; age at start of rehabilitation; time since SCI. Further variables include smoking status (current smoker, former smoker, non-smoker), and pack-years; individual medication use and vaccination (particularly against influenza); and also influenza activity in the local community. Some variables may also induce mediating effects, which can be evidenced by targeted mediation analysis, or cause moderating effects, which can be verified by investigating interaction terms with specific predictor variables. In defining the actual modelling strategy, which particularly includes accounting for extraneous and confounding variables in the estimation of effect sizes for predictor variables, we will make use of the graphical software DAGitty (31).

Continuous variables, such as age and time since injury, may show a nonlinear relationship with the primary outcome or secondary outcomes. To formally evaluate and model nonlinear associations for these variables we will use multivariable fractional polynomial regression as well as piecewise/spline regression techniques in the modelling of survival time (27, 32).

Handling of sampling bias and attrition bias

As any observational study in a clinical setting, RESCOM may suffer from sampling bias, implying that the study population is not a random selection from the target population. Furthermore, attrition bias may occur, implying the selective dropout of study participants. Various factors may principally account for sampling bias as well as attrition bias, including the subjects' cultural background, gender, age, or socioeconomic status.

Descriptive and statistical approaches to evaluate and counteract sampling or attrition bias:

- Comparative descriptive analysis of baseline characteristics of eligible population that was initially invited to participate to the study with effective study participants. If appropriate, use of inverse probability weighting (derived from propensity scores for study participation) in weighted regression analysis
- Evaluation of selective attrition in relation to baseline characteristics. Again, inverse probability
 weighting for longitudinal studies can be used to counterweigh potential developing attrition bias in
 regression analysis.

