7.1 Project flow chart(s) / table of procedures and assessments

7.2 Assessments of primary endpoint/outcome

The primary endpoint of this study is the diagnostic accuracy of inspiratory muscle strength for predicting or excluding clinical pneumonia. Diagnostic accuracy of positive and negative results will be evaluated by the area under the receiver operating characteristic (ROC) curve, which provides an operational measure of the intrinsic ability of the diagnostic test by offsetting the true positive rate against the false positive rate (13). Based on our previous evidence, MIP was defined as the primary diagnostic lung parameter (14). The potential additive diagnostic value of various other lung parameters, including forced vital capacity (FVC), forced expiratory volume in 1 second (FEV₁), peak expiratory flow (PEF), peak cough flow (PCF) and maximum expiratory muscle strength (MEP) will also be investigated. The two measures for the primary endpoint, maximal inspiratory pressure (MIP) and the event of clinical pneumonia, are assessed as follows.

Inspiratory muscle strength will be measured using a hand-held respiratory pressure meter (Micro RPM, Micro Medical, Hoechberg, Germany) by an independent study nurse of each participating study site. All measurements will be performed with the patients sitting upright in their own wheelchair. Patients have to breathe through a mouthpiece while wearing a nose clip. Each measurement will be repeated three times. The greatest value of each parameter will be used for analysis (15).

For each event of pneumonia the following information will be recorded: date of event; duration of event; physician diagnosed; and type. The differentiation of the type of pneumonia is important and will be evaluated using patients medical records data following the pneumonia flow diagram of "Disease and Control Prevention / National Healthcare Safety surveillance definition of health care—associated infection and criteria for specific types of infections in the acute care setting" (16). To determine the type of pneumonia the methods x-ray, signs and symptoms and the laboratory are used. Finally four different types of pneumonia can be diagnosed.

Pneumonia 1: clinically defined pneumonia

Pneumonia 2: pneumonia with common bacterial or filamentous fungal pathogens and specific lab findings

Pneumonia 3: pneumonia with viral and other uncommon pathogens and specific lab findings Pneumonia 4: pneumonia in immunocompromised patients

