8. STATISTICAL METHODOLOGY

8.1 Determination of Sample Size (STROBE 10)

Regarding the in- and exclusion criteria, we made a calculation of a realistic numbers of subjects who can be recruited for this study per year and center, based on the number of patients admitted to the corresponding center during the last years.

Estimated numbers of patients per year for each center are as follows:

Switzerland:	SPZ Nottwil:	30 patients
	Balgrist Zürich:	20 patients
	Rehab Basel:	20 patients
	CRR Sion:	5 patients
Germany:	BG Hamburg:	30 patients
Austria:	Haering:	30 patients
	Tobelbad:	30 patients
Australia:	Heidelberg:	45 patients
The Netherlands:	Rijndam:	20 patients

Heliomare: 20 patients

Overall, we will be able to recruit about 250 patients per year for this study.

Overall sample size: 625 patients

With an anticipated number of 625 subjects over a 2.5 years recruitment period, we may detect about 250 cases of pneumonia (under the assumption of a 40% incidence rate (6, 7).

Moreover, taking the diagnostic accuracy (i.e., area under the curve (AUC)) of 0.86 from a retrospective study as reference (14), the envisioned sample size of at least 250 cases per diagnostic group should allow for detecting a diagnostically and clinically relevant effect (i.e., change in AUC) of 0.07 to 0.05 with 95% confidence level and 80% power (18).

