8.3.1 Datasets to be analysed

Regression analyses of the primary outcome and secondary outcomes may suffer from missing data, which may cause bias and loss of information in analyses that are restricted to study participants with complete data ("complete-case analyses"). To appropriately account for missing data in advanced regression analyses we will use multiple imputation techniques as well as an iterative imputation method (missForest) based on a random forest (33, 34).

Due to the relatively high anticipated sample size, the analysis will be split up into specific sub-groups (e.g. completeness of lesion, para-/tetraplegia, type of pneumonia). For mortality flexible parametric modeling of survival data) and other secondary outcome analyses will be performed Handling of missing data

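### The planned gain in AUC from combining other markers and covariates with MIP has no internal validation, so as written it would be biased upward: slightly in the full cohort, more in small sub-groups

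*Combined protocol and SAP*

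**What the plan says.** Section 7.2 names MIP as the primary diagnostic parameter and adds a further aim without any condition: "The potential additive diagnostic value of various other lung parameters", listed as FVC, FEV1, PEF, PCF and MEP, will be studied.

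Section 8.3.2 (Advanced regression modelling), under general principles, gives multivariable ROC analysis as the model for the primary outcome. Its part on the primary outcome plans covariate-adjusted ROC methods. For the case where covariates change the ROC curve itself, it points to estimators that "combine marker and covariate information in describing the improvement in discriminatory accuracy". The same section lists candidate predictors and covariates and allows interaction terms and fractional polynomials. Section 8.3.1 (Datasets to be analysed) adds that "the analysis will be split up into specific sub-groups", without giving sizes.

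There is one cohort ("Overall sample size: 625 patients"). No section describes a hold-out sample, cross-validation, bootstrap, optimism correction or shrinkage. Section 8.3.2 (Ancillary analysis) offers only a non-parametric ROC and a comparison of imputed with complete data. Section 3.2 speaks of replicating the MIP cut-off concept across settings, not of validating a combined rule.

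**The concern.** A combination whose weights are estimated from the data nearly always shows a higher AUC in those data than MIP alone, even if the added variables carry no information. In new patients the same combination does slightly worse than MIP, because the estimated weights add noise. The bias grows with the number of terms and as the number of cases falls. Covariate adjustment does not remove it.

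At stake is the secondary message of the primary-outcome paper: whether a battery of lung tests plus patient characteristics discriminates better than MIP. Section 8.3 sets a significance level of 0.05, but no section names a test of added value. An ordinary paired comparison of two AUCs, one of them from a score fitted to the same data, therefore remains open, and it can be badly anti-conservative. The AUC of MIP as a single unweighted marker is not in question.

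**Working it through.** **Inputs from section 8.1.** 625 patients and 40% incidence give 625 × 0.40 = 250 cases and 375 non-cases. The reference is an "area under the curve (AUC)) of 0.86 from a retrospective study as reference". The stated detectable effect, based on "the envisioned sample size of at least 250 cases per diagnostic group", is a "change in AUC) of 0.07 to 0.05 with 95% confidence level and 80% power".

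**The plan's own figure.** Use the binormal variance V(A) = 0.0099·exp(-a²/2)·[(5a² + 8) + (a² + 8)/R], with a = 1.414·z(A) and R non-cases per case. Take two-sided 5% (sidedness is not stated) and 80% power.
- One AUC against 0.86, R = 1: V(0.86) = 0.0925 and V(0.91) = 0.0617. Then n = (1.96·√0.0925 + 0.842·√0.0617)² / 0.05² ≈ 259 cases for a change of 0.05.
- Two independent AUCs, R = 1: V(0.93) = 0.0473. Then n = (1.96·√(2 × 0.0925) + 0.842·√(0.0925 + 0.0473))² / 0.07² ≈ 273 cases for a change of 0.07.
- Solving for the upward change at 250 cases, with R from 1 to 1.5, gives 0.051 to 0.048 (one AUC) and 0.073 to 0.069 (two independent AUCs).

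The stated range is reproduced.

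**Simulation.** MIP, oriented so that a higher score means higher risk, is normal in both groups with means √2·z(0.86) apart, so its AUC is 0.86. The k added variables, correlated 0 or 0.5 with MIP, carry no information beyond it, so the ideal combination gains exactly 0. A logistic combination is fitted with main effects only. The gain is its AUC minus that of MIP. It is computed in the same data (apparent), after a bootstrap optimism correction, and in large samples of new patients.

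**Number of terms (assumed).** The five markers give k = 5. Counting AIS grade (3), lesion level (1), partial ventilation (1), gender, age, time since injury, pack-years, vaccination and influenza activity (1 each) and smoking (2) adds 3 + 1 + 1 + 6 + 2 = 13, so k = 18. A second run used 5 + 11 = 16.

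| Cases / non-cases | k | Apparent gain | Bootstrap-corrected | New patients | Naive paired AUC test, rejections | Nested likelihood-ratio test, rejections |
|---|---|---|---|---|---|---|
| 250 / 375 | 5 | +0.003 | -0.003 | -0.003 | 0–2% | 3–8% |
| 250 / 375 | 16 | +0.009 | not run | -0.009 | about 49% | 3–4% |
| 250 / 375 | 18 | +0.010 | -0.009 | -0.010 | about 60% | 3–8% |
| 100 / 150 (assumed) | 18 | +0.024 | -0.021 | -0.025 | 59% | 5% |
| 50 / 75 (assumed) | 5 | +0.013 | -0.014 | -0.013 | 1% | 5% |
| 50 / 75 (assumed) | 18 | +0.050 | -0.031 | -0.051 | 78% | 13% |

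In the full cohort the apparent gain was above zero in 99 to 100% of data sets. With 200 data sets per full-cohort scenario at k = 5 and 18, the Monte Carlo error of a 5% rate is √(0.05 × 0.95/200) = 1.5 points, so 3 to 8% is compatible with 5%. In the 50/75 setting with 18 terms, 43% of data sets showed an apparent gain of 0.05 or more.

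**Sensitivity.** With an AUC of 0.75 for MIP in the full cohort, the apparent gain is 0.005, 0.012 and 0.018 for 5, 12 and 20 terms. With an AUC of 0.86, 20 terms and an assumed incidence of 20% or 10%, it is 0.015 or 0.024.

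**The case against.** **The plan commits to no fitted score.** The sentence on combining markers and covariates is conditional and describes methods that exist. Evaluation in the same patients is inferred from silence. That stands as a limit on the wording. It does not remove the point: the aim in section 7.2 is unconditional, multivariable ROC analysis is named as the primary-outcome model, and with one cohort and no validation step an apparent gain is what the analysis would produce.

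**The effect is small at the plan's own figures.** This stands. In the full cohort the false gain is 0.003/0.05 = 6% to 0.010/0.05 = 20% of the lower end of the change that section 8.1 calls relevant.

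**The null case is extreme.** Section 3.1 reports that level and completeness of injury predict pulmonary complications, so not all covariates are noise. This stands for the rejection rates, which apply only when nothing is added. If some covariates are informative, the apparent gain still overstates what the fitted score achieves in new patients; that case was not simulated.

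**No AUC-versus-AUC test is planned.** True; the risk is that none is excluded. For the five lung markers alone, such a test was conservative.

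**A stronger reading.** A reader might infer that in sub-groups the false gain routinely matches the 0.05 to 0.07 of section 8.1. The documents do not support this. They give no sub-group sizes, do not say that a many-term combination is refitted in each sub-group, and do not define that range as a gain over MIP in the same patients. In assumed sub-groups of 60/250 and 30/280 with 16 terms, the apparent gains were 0.0253 and 0.0391. Figures of 0.052 and 0.080 arise only by subtracting the negative new-patient gains (0.0253 + 0.0263 and 0.0391 + 0.0405), and the published report would show the apparent gain.

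**Conclusion.** The point holds in a limited form. As written, the improvement over MIP would be an apparent gain with upward bias. At 250 cases, 375 non-cases and an AUC of 0.86, with nothing truly added, it averages about +0.003 with five markers and about +0.01 with 16 to 18 terms. The gain in new patients is about -0.003 and -0.01. The main practical risk in the full cohort is a naive paired AUC test, which would reject in roughly half or more of null data sets with 16 to 18 terms but in only about 0 to 2% with the five markers.

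The false gain approaches 0.05 only in small sub-groups with many terms, such as the assumed 50/75. These sizes rest on assumed term counts and sub-group sizes and on main effects only; interactions, fractional polynomials or data-driven selection would increase the optimism. This is a reporting weakness in an additional aim, worth correcting before analysis. It would be wrong to infer that the primary result is compromised: the AUC of MIP as a single marker has no fitted weights and is unaffected.

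**What to change.** In section 8.3.2 (Advanced regression modelling), for any combined marker:

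- Pre-specify the terms and their degrees of freedom.
- Report its AUC and its gain over MIP with a bootstrap optimism correction, or repeated cross-validation, that repeats imputation, choice of functional form and any selection in each resample.
- Test added value with a nested-model test of the pre-specified terms, allowing for clustering and pooled over imputations. Do not use a comparison of two AUCs when one comes from a score fitted to the same data.
- Label combined-marker results in small sub-groups exploratory. In the 50/75 setting with 18 terms the bootstrap under-corrected (-0.031 against -0.051 in new patients) and the likelihood-ratio test was somewhat liberal (13%).

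Leave-one-clinic-out may be added as a check of transport between clinics, but not as the main correction. The smallest clinic expects 5 × 2.5 = 12.5 patients, or about 12.5 × 0.40 = 5 cases.

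The cost is SAP wording and computing time; no new data are needed, and section 8.3.3 already allows the analysis protocol to be updated. The downside is a slightly smaller reported gain.
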